# 3. INVESTIGATIONAL PLAN

# 3.1. Summary of Study Design

This is a randomized, placebo-controlled, double-blind, multi-center, multinational, Phase 2 study to evaluate the efficacy, safety, PD, and PK of lumasiran administered SC in patients with recurrent calcium oxalate kidney stone disease and elevated urinary oxalate levels (Figure 1).

The study will consist of up to 2 months of screening and 15 months of double-blind treatment (a 6-month Primary Analysis Period followed by a 9-month Treatment Extension Period). Patients will be screened from Day -60 to Day -1 to determine eligibility. During screening, patients will provide at least two 24-hour urine collections to establish baseline urinary oxalate levels. Consented patients meeting all eligibility criteria will be randomized 1:1:1 to receive study drug: lumasiran 567 mg, lumasiran 284 mg, or placebo. Stratification will be performed at randomization according to baseline urinary oxalate level ( $\leq 1.25 \times ULN \text{ vs} > 1.25 \times ULN$ ) from the mean of the first 2 valid 24-hour urine collections and the number of historical kidney stone events in the 12 months prior to screening ( $\leq 1 \text{ vs} > 1$ ), as discussed in Section 3.4.

During the 6-month Primary Analysis Period, patients will be dosed on Day 1 (baseline) and at Month 3. During the Treatment Extension Period, one additional dose will be administered at Month 9; an end of study (EOS) visit will take place at Month 15. Study drug will be administered SC as specified in Section 5.2.2. Patients will be assessed for efficacy, safety, PD, and PK according to the Schedule of Assessments (Table 1 and Table 2). Efficacy assessments will include evaluation of urinary oxalate excretion, urinary calcium oxalate supersaturation, and kidney stone events (including clinical events and radiologic events with optional low-dose kidney-protocol CT). Safety assessments will include collection of AEs, clinical laboratory tests, vital sign assessments, physical examinations, and concomitant medications.

Patients who discontinue study drug early will be asked to return for follow-up visits as described in Section 4.3.1.

# 3.2. Scientific Rationale for Study Design

The primary endpoint for this Phase 2 study is the percent change in 24-hour urinary oxalate excretion. To confirm the optimal dosing regimen, and to facilitate the collection of kidney

stone event data (an exploratory endpoint), the study will continue through Month 15. A placebo comparator is included because there is no approved standard of care therapy to decrease urinary oxalate.

A blood DNA sample will be collected as part of standard screening assessments (if testing has not already been performed) to ensure the exclusion of patients with primary hyperoxaluria type 1 (PH1), type 2 (PH2), and type 3 (PH3). Lumasiran is approved in some countries for the treatment of PH1, and patients with PH2 and PH3 are not expected to respond to lumasiran.

Because the primary endpoint will rely on measurements of urinary oxalate, and because some urinary oxalate is diet-derived, diet is an important variable in this study. In a 5-year study of recurrent stone formers published by Borghi et al, patients randomized to a normal calcium, low protein/salt diet had lower urinary oxalate levels and a lower cumulative incidence of recurrent kidney stones when compared to a low calcium diet. During the current study, and as of the time of informed consent, patients will be asked to adhere to a diet appropriate for stone formers, including adequate calcium intake and avoidance of spinach and other foods that are high in oxalate.

The secondary endpoint to assess meaningful reduction in 24-hour urinary oxalate from baseline to Month 6 (Months 4 through 6) defines a clinically meaningful reduction as ≥20% in the non-PH1 stone former population, supported by available literature based on stone former populations.[Borghi 2002]

In this study, lumasiran will be evaluated in patients with recurrent calcium oxalate kidney stone disease. Due to the limited and burdensome disease management options, there is an unmet need for new therapies.

# 3.3. Justification for Dose

Two dose levels of lumasiran 284 and 567 mg given on Day 1, Month 3, and Month 9 were selected to evaluate urinary oxalate dose response. The higher dose level of 567 mg is expected to suppress GO enzyme by ≥95%, comparable to the regimen evaluated in ALN-GO1-003 (ILLUMINATE-A) in patients with PH1. The lower dose of 284 mg is expected to suppress GO enzyme by 90%. In addition, the fixed doses will simplify dose administration in this adult study population. Both regimens are predicted to achieve near-steady state ribonucleic acid-induced silencing complex (RISC) concentrations and urinary oxalate suppression at Month 6. Month 9 dosing is intended to sustain PD effect through Month 15 and will provide data to differentiate the effect of every 3 months and every 6 months dosing on urinary oxalate reduction.

Single 0.3 to 6.0 mg/kg doses of lumasiran in healthy subjects and multiple 3.0 mg/kg doses of lumasiran administered monthly or once every 3 months in patients with PH1 have been well tolerated. Plasma and liver exposure for the lumasiran 284 and 567 mg doses are expected to be in the range of 3.0 to 6.0 mg/kg lumasiran doses evaluated in healthy subjects in ALN-GO1-001 (Part A) and patients with PH1 in ALN-GO1-001 (Part B), ALN-GO1-002, and ILLUMINATE-A. Based on rat and monkey NOAEL doses of lumasiran 200 mg/kg and 300 mg/kg, a sufficient safety margin exists for the use of lumasiran 284 and 567 mg doses (refer to the ALN-GO1 Investigator Brochure).

Based on a 70 kg patient, the planned doses of 284 mg and 567 mg equate to approximately 4.0 mg/kg or 8.0 mg/kg, respectively. The human equivalent dose (HED) margin values for the

approximate 4 mg/kg clinical dose were 8.1-fold for the chronic rat study and 24.2-fold for the chronic monkey study; the HED margin values for the approximate 8.0 mg/kg clinical dose were 4.0-fold for the chronic rat study and 12.1-fold for the chronic monkey study (refer to the ALN-GO1 Investigator Brochure).

# 3.4. Method of Assigning Patients to Treatment Groups

Each patient will be uniquely identified in the study by a combination of the site number and patient identification number. After the patient signs the informed consent form (ICF) and before proceeding with screening procedures, the Investigator or his/her designee will contact the Interactive Response Technology (IRT) to obtain a patient identification number.

The Investigator or his/her designee will contact the IRT to randomize the patient after confirming that the patient fulfills all the inclusion criteria and none of the exclusion criteria.

Patients will be randomized 1:1:1 to receive lumasiran 284 mg, lumasiran 567 mg, or placebo, administered at the same volume (see Section 5.2.2), for the duration of the study. Stratification will be performed at randomization according to baseline urinary oxalate level ( $\leq 1.25 \times ULN$ ) vs >1.25 × ULN) from the mean of the first 2 valid 24-hour urine collections and the number of historical kidney stone events in the 12 months prior to screening ( $\leq 1 \text{ vs} > 1$ ).

For stratification, the number of historical kidney stone events occurring in the 12 months prior to screening are considered, and defined as:

- the visible passage of a kidney stone
- a procedural intervention for removal of an asymptomatic or symptomatic stone
  - if more than 1 stone was removed in a given procedure, this counts as 1 event unless bilateral ureteral stones were removed, in which case this counts as 2 events
  - if more than 1 procedure was required to remove a single stone, this counts as
     1 event
- a new ( $\ge 1$  mm) or enlarged (by  $\ge 2$  mm) kidney stone on CT imaging
  - it must be evident from the CT scans that the new or enlarged kidney stone event occurred during the 12 months prior to screening
  - if a procedure was performed to remove the stone(s) identified by CT, then only
    the procedure will be counted to avoid double-counting the same stone.

# 3.5. Blinding

Site personnel and patients will be blinded to study drug treatment; site personnel preparing study drug may be unblinded to study drug treatment only where required by documented institutional procedure. The Sponsor will have access to unblinded study data during the conduct of the study. Lumasiran and placebo will be packaged identically and will be administered at the same volume under the supervision of the Investigator at the study center or by a healthcare professional at the patient's home (see Section 5.2.2). Since lumasiran may be visually

distinguishable from placebo, the syringe will be masked prior to administration by a healthcare professional. See the Pharmacy Manual for additional details.

All site personnel will be blinded to laboratory results of oxalate, calcium oxalate supersaturation, and glycolate from after the time of the first dose until unblinding. Results will not be reported to the Investigator from the first dose until the last patient completes assessments at the Month 15 visit. In addition, Investigators and staff involved with this trial and all medical staff involved in the patient's medical care should refrain from obtaining measurements for oxalate, calcium oxalate supersaturation, or glycolate from the first dose until the sites and patients are unblinded, or until the patient ends the study, whichever is earlier. If oxalate, calcium oxalate supersaturation, or glycolate are measured during the blinded period, all reasonable steps must be undertaken to avoid informing the patient and site personnel of the results until the sites and patients are unblinded.

Any unplanned unblinding occurring during the study period will be documented and reported in the clinical study report.

### 3.5.1. Emergency Unblinding

If the treating physician determines that the clinical management of the patient requires knowledge of the study drug assignment, the Investigator may break the blind, as necessary. If time permits, clinical study center personnel should contact the Medical Monitor before unblinding to discuss the need to unblind the patient. If contact prior to unblinding is not possible, personnel must contact the Medical Monitor within 1 working day after the unblinding event. Unblinding information should be limited to the fewest number of people on a need-to-know basis. A record of when the blind was broken, who was unblinded, who broke the blind, and why it was broken, will be maintained in the trial master file.

Refer to the IRT instructions for details on unblinding.

# 3.6. Safety Review

A safety review committee will not be utilized for this study; however, the Sponsor will monitor safety on an ongoing basis and in accordance with the Sponsor's internal processes.

# 3.7. Definition of End of Study for an Individual Patient

A patient is considered to have reached the EOS if the patient:

- has completed the EOS (Month 15) visit, or
- has completed safety monitoring following the final dose of study drug as described in Section 4.3.1

A definition of the end of the overall study is provided in Section 8.1.5.

### 4. SELECTION AND REMOVAL OF PATIENTS

# 4.1. Inclusion Criteria

Patients are eligible to be included in the study if all the following criteria apply:

### Age

1. Age 18 years or older (or age of legal consent, whichever is older).

### **Patient and Disease Characteristics**

- 2. Recurrent kidney stone disease, defined as ≥2 stone events, with a minimum of 1 stone event within the 5 years prior to screening. For inclusion, a historical kidney stone event is defined as:
  - the visible passage of a kidney stone
  - a procedural intervention for removal of an asymptomatic or symptomatic stone
    - if more than 1 stone was removed in a given procedure, this counts as 1 event unless bilateral ureteral stones were removed, in which case this counts as 2 events
    - if more than 1 procedure was required to remove a single stone, this counts as
       1 event
  - a new ( $\ge 1$  mm) or enlarged (by  $\ge 2$  mm) kidney stone on CT imaging
    - if a procedure was performed to remove the stone(s) identified by CT, then only
      the procedure will be counted to avoid double-counting the same stone.
- 3. The 2 most recently analyzed kidney stones prior to randomization contained 50% or more of calcium oxalate; if only one stone analysis is available, then it must have contained 50% or more of calcium oxalate.
- 4. 24-hour urinary oxalate levels from 2 valid 24-hour urine collections obtained during screening are >ULN (ULN = 40 mg/24 hours).
- 5. Willing to adhere to dietary recommendations appropriate for stone formers including limiting vitamin C supplementation to <200 mg daily.
- 6. If taking medications and/or hydrating for kidney stone prophylaxis, or taking medications that alter urinary oxalate excretion and/or kidney stone formation, must have been on a stable regimen for at least 60 days before randomization, and willing to remain on this stable regimen for the duration of the study.
- 7. Body mass index (the weight in kilograms divided by the square of the height in meters) at screening of 20 to  $<40 \text{ kg/m}^2$ .

### **Informed Consent**

8. Patient is able to understand and is willing and able to comply with the study requirements and to provide written informed consent.

# 4.2. Exclusion Criteria

Patients are excluded from the study if any of the following criteria apply:

# **Laboratory Assessments**

- 1. Has any of the following laboratory parameter assessments at screening:
  - a. Alanine aminotransferase (ALT) or aspartate aminotransferase (AST) >2 × ULN
  - b. Total bilirubin >1.5  $\times$  ULN. Patients with elevated total bilirubin that is secondary to documented Gilbert's syndrome are eligible if the total bilirubin is  $<2 \times$  ULN
  - c. International normalized ratio (INR) >2.0 (patients on oral anticoagulant [eg, warfarin] with an INR <3.5 will be allowed)
- 2. Has an eGFR of <30 mL/min/1.73m^2 at screening (calculation will be based on the Chronic Kidney Disease Epidemiology Collaboration [CKD-EPI] creatinine formula; see Section 10.1).

# **Prior/Concomitant Therapy**

3. Received an investigational agent within the last 30 days or 5 half-lives, whichever is longer, prior to the first dose of study drug, or are in follow-up of another clinical study prior to study enrollment. Any agent that has received health agency authorization (including for emergency use) by local or regional regulatory authorities is not considered investigational.

### **Medical Conditions**

- 4. Patients with a known history of secondary causes of elevated urinary oxalate and/or recurrent kidney stones including:
  - a. Primary hyperoxaluria
  - b. Severe eating disorders (anorexia or bulimia)
  - c. Chronic inflammatory bowel disease
  - d. Intestinal surgery with malabsorption or chronic diarrhea
  - e. Sarcoidosis
  - f. Primary hyperparathyroidism
  - g. Complete distal renal tubular acidosis
- 5. Has other medical conditions or comorbidities which, in the opinion of the Investigator, would interfere with study compliance or data interpretation.
- 6. History of multiple drug allergies or history of allergic reaction to an oligonucleotide or GalNAc.
- 7. History of intolerance to SC injection(s).

# Contraception, Pregnancy, and Breastfeeding

- 8. Is not willing to comply with the contraceptive requirements during the study period, as described in Section 5.6.1.
- 9. Female patient is pregnant, planning a pregnancy, or breast-feeding.

### Alcohol Use

- 10. Unwilling or unable to limit alcohol consumption throughout the course of the study. Alcohol intake of >2 units/day is excluded during the study (unit: 1 glass of wine [approximately 125 mL] = 1 measure of spirits [approximately 1 fluid ounce] = ½ pint of beer [approximately 284 mL]).
- 11. History of alcohol abuse, within the last 12 months before screening, in the opinion of the Investigator.

# 4.3. Removal from Study Drug or Assessment

Patients are free to discontinue study drug and/or stop protocol procedural assessments, or participation in the study as a whole at any time and for any reason, without penalty to their continuing medical care. The Investigator or the Sponsor may discontinue study drug or stop a patient's participation in the study at any time if this is considered to be in the patient's best interest. Any discontinuation of treatment or the stopping of the patient's participation in the study must be fully documented in the electronic case report form (eCRF) and should be followed up by the Investigator.

Discontinuation of study drug or declining procedural assessments is described in Section 4.3.1, while the stopping of a patient's participation in the study is detailed in Section 4.3.2.

# 4.3.1. Discontinuation of Study Drug or Declining Procedural Assessments

Reasons for discontinuation of study drug include any of the following:

- Significant protocol deviation
- Adverse event
- Non-adherence to treatment regimen
- Pregnancy
- Lost to follow-up
- Other reason (non-AE)
- Or, study is terminated by the Sponsor

If possible, the Investigator will confer with the Sponsor or Medical Monitor before discontinuing dosing in the patient. Patients who are pregnant will be discontinued from study drug dosing immediately (see Section 6.5.5.7 for reporting and follow-up of pregnancy). A positive urine pregnancy test should be confirmed by a serum pregnancy test prior to discontinuing the study drug.

Patients who discontinue study drug and/or decline procedural assessments should not be automatically removed from study. In general, patients who discontinue study drug dosing for any reason will be encouraged to remain on the study to complete the remaining assessments so that their experience is captured in the final analyses.

If this occurs, the Investigator is to discuss with the patient the appropriate processes for discontinuation from study drug and must discuss with the patient the options for continuation of

the Schedule of Assessments (Table 1), including different options for follow-up and collection of data (eg, in person, by phone, by mail, or from options not involving patient contact, such as communication with other treating physicians or from review of medical records), including endpoints and AEs, and must document this decision in the patient's medical records.

If a patient discontinues dosing due to an AE, including serious adverse events (SAEs), the event should be followed as described in Section 6.5.5. When a patient discontinues study drug dosing, the primary reason must be recorded in the eCRF. Patients who discontinue study drug and remain on study may receive treatment consistent with local standard practice for their disease per Investigator judgement, as applicable.

Patients who discontinue from study drug during the 6-month Primary Analysis Period (defined as a discontinuation that occurs after the first dose of study drug administration on Day 1 during the 6-month Primary Analysis Period) will be encouraged to remain on the study and complete all assessments (including 24-hour urine collections) through Month 6, with early termination (ET) assessments at Month 9, and safety follow-up per the safety follow-up schedule (Table 1). Patients who do not remain on the study through Month 6 will be asked to return for their next scheduled visit to complete ET assessments and complete safety follow-up per the safety follow-up schedule (Table 1).

Patients who discontinue study drug after Month 6 will be asked to return for their next scheduled visit to complete ET assessments and complete a safety follow-up visit per the safety follow-up schedule (see Table 1).

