Single 24-hour urine collection	Collect within 14 days prior to dosing (M3) or visit (M4, M5, M6); repeat if invalid. See Table 4			х	х	Х	Х			
Blood sample for PD analyses	Section 6.3	X	X	X			X	X	X	
Clinical laboratory assessments	Section 6.5.4	X	X	X			X	X	X	X
Antidrug antibody sample	Section 6.5.4.1		X	X			X	X	X	X
Urine pregnancy test (for WOCBP) c	May be performed more frequently where required per local requirements, or if pregnancy is suspected. See Section 6.5.4.2		х	X				Х		
Symptom-directed physical examination	Section 6.5.3		X	X				X		X
Prior and concomitant medications	Section 5.4		Continuous							

Table 1: Schedule of Assessments

			1	5 Monti Treati	h Doub nent Pe		I			
		Screening	Pri	mary A	nalysis l	Period		Treat Exter Per	nsion	Safety
Study Visit			Baseline	М3	M4	MS	М6	ЕОТ М9	EOS/ ET M15	Follow-up (Patients who D/C Treatment Early)
Study Day (±Visit Window)	Notes	-60 to -1	Day 1	85 (±14)	113 (±7)	(41 (±7)	169 (±14)	253 (±28)	421 (±28)	3 and 6 months post last dose (±28)
Clinical kidney stone events	Section 6.2.2				C	ontinuo	us			
Review/record adverse events	Section 6.5.5				C	ontinuo	us			
Healthcare utilization	Section 6.6				C	ontinuo	us			
Randomization	Window: 1 business day prior to Day 1 for study drug preparation		X							
Blood samples for PK analyses	Table 2; Section 6.4		X							
Study drug administration	Section 5.2.2		X	X				X		
Optional low-dose kidney- protocol CT scan d	Section 6.2.2.2		X (-3 days window)			1 64			X	

Abbreviations: CT=computed tomography; D/C=discontinue; ET=early termination; EOS=end of study; EOT=end of treatment; M=month; PD=pharmacodynamic; PK=pharmacokinetic; WOCBP=women of child-bearing potential Notes:

- When scheduled at the same time points, assessments of vital signs should be performed before physical examinations and blood sample collections, where feasible.
- Patients who discontinue study drug dosing for any reason will be encouraged to remain on the study to complete the remaining assessments so that their experience is captured in the final analyses (refer to Section 4.3.1).

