### **5.2.2.** Dose and Administration

Patients will be administered SC injections of lumasiran (284 mg or 567 mg) and/or placebo at the same volume, as described below, on Day 1, Month 3, and Month 9.

Lumasiran 567 mg	Lumasiran 284 mg	Placebo
1.5 mL lumasiran	1.5 mL lumasiran	1.5 mL placebo
1.5 mL lumasiran	1.5 mL placebo	1.5 mL placebo

Study drug injections will be administered under the supervision of the Investigator or healthcare professional. To maintain the blind, syringes are to be masked prior to the removal of study drug from vials. A full description of the blinding procedure is included in the Pharmacy Manual. The injection site may be marked and mapped for later observation. Injections may be administered in the abdomen, thigh, or the side or back of the upper arms. If a local reaction around the injection site occurs, photographs may be obtained. Detailed instructions for study drug administration are found in the Pharmacy Manual.

Dosing will be permitted at a location other than the study center (for example, the patient's home) by a healthcare professional with the oversight of the Investigator, provided the patient has tolerated at least 1 dose of study drug administered in the clinic. However, continued study

drug administration at the study center should be considered for patients who have ongoing study drug-related AEs or for anyone in the opinion of the Investigator who would benefit from clinical observation following dosing.

If a patient does not receive a dose of study drug within the specified visit window, the Investigator should contact the Medical Monitor. After such consultation, the dose may be administered or considered missed and not administered.

Additional details can be found in the Pharmacy Manual.

The definition of study drug overdose, follow-up procedures, and reporting requirements are provided Section 6.5.5.8.

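### Section 4.3.1 both keeps patients who stop study drug before Month 9 for the remaining assessments and sends them out by Month 9, so the exploratory Month 15 comparison omits them

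*Protocol*

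**What the plan says.** The general rule in Protocol Section 4.3.1 is that "patients who discontinue study drug dosing for any reason will be encouraged to remain on the study to complete the remaining assessments", and its stated purpose is "so that their experience is captured in the final analyses". The notes under Table 1 repeat it: such patients "will be encouraged to remain on the study to complete the remaining assessments so that their experience is captured in the final analyses".

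The specific rules come later in Section 4.3.1:

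- **Stop during the Primary Analysis Period, patient stays:** the patient is encouraged to "complete all assessments (including 24-hour urine collections) through Month 6, with early termination (ET) assessments at Month 9", then enters safety follow-up.
- **Stop during the Primary Analysis Period, patient does not stay to Month 6:** ET at the next scheduled visit, then safety follow-up.
- **Stop after Month 6:** "Patients who discontinue study drug after Month 6 will be asked to return for their next scheduled visit to complete ET assessments", then safety follow-up.

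In Table 1, safety follow-up falls 3 and 6 months after the last dose and has no 24-hour urine collection. Section 3.7 treats a patient who has finished that follow-up as having reached end of study. Doses are given "as described below, on Day 1, Month 3, and Month 9" (Section 5.2.2).

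Month 15 data have a stated use. Section 3.2 continues the study to Month 15 to confirm the regimen and collect stone events. Section 3.3 says the Month 9 dose "will provide data to differentiate the effect of every 3 months and every 6 months dosing on urinary oxalate reduction". Section 7.2.5 compares lumasiran with placebo on oxalate at Months 9 and 15.

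**The concern.** The general rule promises that patients who stop drug will be represented in the final analyses. The specific rules, followed literally, end data collection by Month 9 for anyone who stops before the Month 9 visit. A site can comply with either text, so Month 15 retention of these patients may vary by site.

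What is at stake is which patients the Month 15 comparison describes. It is presented on the full analysis set by randomized arm, but it would contain no early stoppers. Nothing downstream compensates:

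- SAP Section 4.3 plans no explicit imputation.
- SAP Table 2 lists vitamin C use as the only intercurrent event.
- SAP Section 5.7.3.1 censors time to first stone event at study discontinuation, so leaving because drug was stopped could make that censoring informative.
- Protocol Section 4.3.4 allows no replacement.

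**Working it through.** **Step 1. Apply the rules to each type of patient.** Table 1 gives Month 3 = Day 85, Month 6 = Day 169, Month 9 = Day 253 and Month 15 = Day 421. There is no visit between Months 6 and 9, or between Months 9 and 15.

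- Stops before Month 6 and stays: ET at Month 9. No Month 15 visit.
- Stops before Month 6 and does not stay: ET at the next visit, Month 6 at the latest. No Month 15 visit.
- Stops after Month 6 but before the Month 9 visit: the next visit is Month 9, so ET is there. No Month 15 visit.
- Stops at or after the Month 9 visit: the next visit is Month 15, where end of study and ET share one column. Month 15 data are collected.
- Misses a dose, or has it held, without discontinuing (Section 5.2.2; Table 3): continues to Month 15.

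The gap is therefore confined to patients who stop before the Month 9 visit.

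**Step 2. What those patients lose.** They have no planned Month 15 urine oxalate and no Month 15 CT if they had opted in. An ET visit after Month 6 may include a CT at the Investigator's discretion (Section 6.2.2.2). The 6-month safety visit after a Month 3 dose falls at about Day 85 + 168 = Day 253 (±28 days), so stone follow-up ends at about Month 9. The lost interval is 421 − 253 = 168 days, out of 421 − 1 = 420, which is 40%.

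**Step 3. What they do not lose.**

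- Primary and secondary endpoints use Months 4 to 6, and early stoppers are asked for urine collections through Month 6.
- Month 9 oxalate: the ET column of Table 1 includes two 24-hour urine collections.
- Stone incidence rate: SAP Section 5.7.3.1 ends time at risk no later than 168 days after the last dose. After a Month 3 dose that is Day 253; after a Day 1 dose only, it is Day 1 + 168 = Day 169. Staying to Month 15 would add no person-time.

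**Step 4. Possible size at Month 15.** The documents give no discontinuation rate. Assume 5-15% per arm stop before Month 9 (2 to 6 of 40), that patients who continue hold a 30-point advantage over placebo, and that those who stopped have none left.

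- Effect in all randomized = 30 × (1 − p), where p is the proportion who stopped.
- Overstatement when they are omitted = 30 × p: 30 × 0.05 = 1.5 points and 30 × 0.15 = 4.5 points.

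**Step 5. A yardstick.** With the planned SD of 45 and 40 per arm, the standard error of a between-arm difference is 45 × √(2/40) = 10.06. This reproduces the plan's own figure: Φ(30/10.06 − 1.96) = 84.7% by the normal approximation and 83.8% by the t-test, against 84% in Table 7. Table 7 concerns Month 6 and is not disputed. If the same SD held at Month 15, the overstatement would be 1.5/10.06 = 0.15 to 4.5/10.06 = 0.45 standard errors.

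**The case against.** The case against is that this is a minor mismatch of wording. The general rule is qualified as applying in general, and a specific rule normally governs. Section 4.3.1 also says that patients who stop drug are not to be removed automatically, and it requires a discussion of follow-up options, including telephone contact and record review. Section 4.3.2.1 repeats that they may stay. Only exploratory analyses are touched. Patients who never received the Month 9 dose say little about six-monthly dosing, and off-drug patients may receive local standard treatment, which would affect a later oxalate value. Following everyone to Month 15 whatever their treatment status is one choice of estimand, and the SAP defines an estimand only for the primary endpoint.

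Much of this stands. It limits the point to exploratory results, and it shows that the missing data follow from a specific instruction and not from a ban on staying. It does not remove the contradiction. The specific rules cover every stop after the first dose, so no patient who stops before the Month 9 visit is left to whom the general rule could apply beyond Month 9. The aim of capturing these patients in the final analyses is the protocol's own.

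A reader might infer that Month 15 data come only from patients still on drug. Step 1 shows otherwise: those who stop at or after Month 9, and those who miss a dose without discontinuing, still reach Month 15. A reader might also infer that the lost follow-up, about 0.9-2.8 of 46 patient-years per arm at 5-15% (2 to 6 × 168/365.25, against 40 × 420/365.25), weakens the stone incidence rate. It does not, because that time is already outside the SAP's definition of time at risk.

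**Conclusion.** The point holds for patients who stop study drug before the Month 9 visit. The passages conflict, and under the specific rules these patients have no planned Month 15 urine oxalate or Month 15 CT, with time to first stone event censored at about Month 9. The exploratory Month 15 comparison should not be read as covering everyone in the full analysis set.

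The illustrated overstatement of 1.5-4.5 points rests on an assumed 5-15% stopping before Month 9, an assumed 30-point effect in those who continue, and complete loss of effect in those who stop. Complete loss makes it an upper bound for any given stopping rate. It is below half a standard error. Informative censoring in the time-to-first-stone analysis is possible, but the documents do not allow it to be quantified.

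The conclusion that Month 9 oxalate is unaffected assumes that an ET collection made at Month 9 is analyzed as Month 9. Table 1 places ET in the Month 15 column, and SAP Section 4.7 uses the visit as reported on the eCRF.

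This is a worthwhile, inexpensive correction. It is not a threat to the trial's main result.

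**What to change.** Reconcile the specific paragraphs of Section 4.3.1 with its general rule and the Table 1 note, for data collection only. Patients who stop study drug and agree to stay would keep the Month 15 urine collections and stone-event follow-up to Month 15, plus the Month 15 CT if they opted in. ET assessments would apply only when a patient leaves the study. No dosing or treatment rule changes.

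The SAP should then say whether off-drug values enter the Month 15 comparison and to which visit an ET urine collection is assigned. If the sponsor prefers to keep the early exit, the general rule and the Table 1 note should be narrowed to match, and the Month 15 results labelled as excluding patients who stopped before Month 9, with the number excluded in each arm.

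The cost is amendment wording and one already-scheduled visit for a few patients (2 to 6 per arm at the assumed 5-15%).
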